7.3. Randomization Assignment: Acoustic Enhancer with Ureteroscopic Laser Lithotripsy (Investigational Arm) vs. Standard Ureteroscopic Laser Lithotripsy (Control Arm)

Following consent and if a subject meets the study's inclusion/exclusion criteria, the subject will be randomly assigned to the investigational or control arm on the day of the procedure. If the potential subject does not meet the study procedure eligibility criteria, he/she will NOT be randomly assigned to treatment or the control arm. Random assignment will be conducted using an allocation ratio of 1:1 with one subject randomized to the Investigational Arm for each subject randomized to the Control Arm. Random assignment will be conducted block design generated separately for each clinical site. Subjects will be blinded to treatment allocation through index procedure.

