10.5. Adjustments for Multiplicity

The study will include a single primary effectiveness endpoint to be tested at the one-sided 0.025 level. If that hypothesis is met, two other endpoints will be considered sequentially. If the first secondary hypothesis is statistically significant, the second hypothesis will also be assessed. Hence, the overall Type I error for the study is controlled for the specified hypotheses.

Secondary Hypothesis 1:

Evaluation of non-inferiority of the normalized total radiant energy (TRE) will be evaluated based on the difference in the means of the log transformed values of the TRE for the investigational and control subjects, respectively. Normalized TRE is the total procedure radiant energy divided by the stop area. A non-inferiority bound of 0.223 will be considered evidence of non-inferiority (see Section 10.7 for discussion of non-inferiority bound). The hypothesis is as follows:

H₀: $\mu_{AE} \ge \mu_{Control} + \delta$ vs H₁: $\mu_{AE} < \mu_{Control} + \delta$

CONFIDENTIAL Page 33 of 53 Where μ_{AE} is the mean of the log of the total radiant energy values for the Acoustic Enhancer, $\mu_{Control}$ is the mean of the log of the total radiant energy values for the Control group, and δ is the non-inferiority bound (δ = 0.223). This will be analyzed using a one- sided 0.025 T-test.

The geometric means for each group will also be displayed by showing the exponentiation of the mean of the log transformed values. Similarly the geometric mean ratio (GMR) and associated 95% CI will be provided by showing the exponentiation of the difference means of the log values and the associated 95% CI values.

Secondary Hypothesis 2:

Reduction in normalized TRE will be analyzed by considering difference in the means log of normalized TRE. The hypothesis is as follows:

 $H_0: \ \mu_{AE} \geq \mu_{Control} \ vs \ H_1: \ \mu_{AE} < \mu_{Control}$

Where μ_{AE} is the mean of the log of the total radiant energy values for the Acoustic Enhancer and $\mu_{Control}$ is the mean of the log of the total radiant energy values for the Control group. This will be analyzed using a one- sided 0.025 test.

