Normalized TRE will be summarized as a numeric variable. In addition, as the primary analysis is based on ratio of the means, the geometric mean and 95% CIs based on the back-transformation of the log values will be provided. The log-transformed values will also be summarized descriptively. All analyses of TRE will be based on available data. TRE is to be collected as part of the procedure and it few if any missing values are expected. If more than 4 subjects have missing TRE values, a MI analysis will be completed as a sensitivity analysis.

In support of the secondary hypotheses (Section 10.5), a t-test will be used to assess the difference in between groups in the means of the log-transformed normalized TRE value. If the two-sided 95% CI upper bound of the difference in the means is less than 0.223 (log 1.25) then secondary hypothesis 1 will be considered met and if bound is less than -0.0, the secondary hypothesis 2 will also be considered met. The one-sided p-values associated with the hypothesis will also be provided.

The ratio cut-off of 1.25 for the non-inferiority assessment was obtained based of review of papers describing total energy (Molina et al (2014), Humphreys et al (2018), and Rana, et al (2020)). Further, discussion with investigators indicated the endpoint could have considerable variability based on uniqueness of the individual subject, stone size, stone composition, and stone location. The Molina (2014) paper included analyses of total energy and found several significant predictors but at best the explained about half the variance (R2 = 0.524 for a multivariate model). Molina (2014) presented an exploration of total energy normalized by stone volume.

CONFIDENTIAL Page 35 of 53

Acoustic Enhancer Research on Laser Lithotripsy (AEROLITH) Clinical Study

Based on normalized TRE from the paper it appears as the ratio of the upper quartile to the median was approximately 1.6. The ratio of 1.25 would reflect a ratio of AE to control that would be close the control mean and well within variability associated with a single standard deviation. Hence, given the inherent variability of the measure, the use of 1.25 as a ratio to indicate non-inferiority normalized TRE is justified.

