The Wilcoxon Rank-Sum test will be used as a confirmatory analysis of the t-test for a comparison of the observed normalized TRE. If more than 4 subjects have missing TRE values, a multiple-imputation analysis will be performed including group and the total stone area as predictive covariates. The homogeneity of the treatment response will be evaluated using a ANOVA model of normalized total radiant power as a function of treatment, study site, and a site-treatment interaction. A p-value of less than or equal to 0.15 in the site-treatment term will be considered evidence of heterogeneity of the treatment effect across sites. In addition, as an exploratory analysis, an ANOVA model will be used if stone location is associated with response or a location-treatment interaction.

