2 STUDY DESIGN AND PROCEDURES

The clinical study is a prospective, multicenter, two-arm, randomized, double blinded study in male or female subjects 18 to 75 years of age with a diagnosis of urinary stone disease. For this study, double blinded means: 1) study subjects will not be informed of their treatment allocation through the index procedure, and 2) in assessing stone fragmentation using a CT image as defined in the primary endpoint, an independent radiologist will conduct the assessment and will be blinded to the treatment allocation of each subject's CT image.

The study visits consist of Screening, Treatment/Procedure [Day 1], Day 14 (+/- 4 days), Day 30 (+14 days), and Day 90 (+/- 21 days). Subjects who have unresolved hydronephrosis at Day 30 need to continue to Day 90. At 90-days post procedure, subjects who have on-going device and/or procedure-related serious adverse events (including device and/or procedure related hydronephrosis) and subjects with pre-existing (prior to treatment) hydronephrosis that have worsened or recurred will continue to be followed until the event has resolved or is deemed stable by the investigator prior to study exit. A total of 196 subjects will be enrolled in this study at up to 27 investigational sites located in the U.S., with each site enrolling no more than 20% of the total.

Following consent and if a subject meets the study's inclusion/exclusion criteria, the subject will be randomly assigned to the investigational arm (Acoustic Enhancer with URS-LL) or

control arm (URS-LL) on the day of the procedure. Random assignment will be conducted using an allocation ratio of 1:1 with one subject randomized to the investigational arm for each subject randomized to the control arm. A minimum of 176 evaluable subjects will be needed for analysis. After randomization and during procedure, eligibility criteria will be verified. If subjects are found to not meet eligibility criteria they will be considered screen failures and will not be considered randomized and treated for analysis purposes.

Random assignment will be conducted using a stratified permuted block design generated separately for each clinical site.

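### Both gated TRE hypotheses rest on an unadjusted t-test; a pre-specified model with site and log stone area could add a few points of power, or nothing

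*Protocol*

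**What the plan says.** Protocol 10.5 places two TRE hypotheses in sequence behind the primary endpoint: non-inferiority with a log-scale bound of 0.223, then reduction. For the first it says "This will be analyzed using a one- sided 0.025 T-test"; for the second it names only a one-sided 0.025 test. Protocol 10.7 settles the method for both: "a t-test will be used to assess the difference in between groups in the means of the log-transformed normalized TRE value". One two-sided 95% confidence interval serves both decisions, with its upper bound compared with 0.223 and then with 0. No site term or covariate is included.

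Randomization is blocked within site in both documents. Protocol 7.3 has "Random assignment will be conducted block design generated separately for each clinical site", and SAP 2 has "Random assignment will be conducted using a stratified permuted block design generated separately for each clinical site". Protocol 8.1 has the size and location of each stone recorded at baseline. Protocol 6.3 and 10.7 divide each subject's laser energy by the summed cross-sectional area of the treated stones.

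Other uses of these variables for TRE in Protocol 10 are not confirmatory. Site enters a homogeneity check, an "ANOVA model of normalized total radiant power as a function of treatment, study site, and a site-treatment interaction". Location enters an exploratory ANOVA. Total stone area is a predictor in an imputation analysis that runs only if more than 4 values are missing. Location and diameter also define stratified summaries in Protocol 10.1.

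SAP 5.1 and 5.2 plan no covariate adjustment, but SAP 8.1.2 and 8.2.3 leave the secondary analysis to a separate plan.

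**The concern.** An analysis that ignores the factor used to block randomization leaves between-site variation in the error term, so precision can be lost. The same holds for a baseline variable that predicts the outcome.

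The protocol itself says in 10.7 that "the endpoint could have considerable variability based on uniqueness of the individual subject, stone size, stone composition, and stone location", without saying whether this refers to energy before or after normalization. Dividing by area removes the size effect only if energy is proportional to area. The paper used to support the margin "presented an exploration of total energy normalized by stone volume", so a residual size effect is possible, though not shown.

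What is at stake is power for the first gated secondary claim, and for the reduction claim that depends on it. The documents state no power for either.

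**Working it through.** **The plan's own figure.** The only stated power is 80% for the primary endpoint (55% vs 75%, 88 per arm, one-sided 0.025). With the pooled null variance: (0.20 − 1.96 × √(2 × 0.65 × 0.35/88)) / √((0.55 × 0.45 + 0.75 × 0.25)/88) = (0.20 − 0.141)/0.0703 = 0.84, which gives 79.96%. Also 176/0.9 = 195.6, rounded up to 196. Both reproduce. For TRE, ln 1.25 = 0.2231 reproduces the bound; there is no power statement to check.

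**Inputs.**
- Spread: Protocol 10.7 reports that "the ratio of the upper quartile to the median was approximately 1.6". If lognormal, log-SD = ln(1.6)/0.6745 = 0.697. This is an assumption, and it describes volume-normalized energy.
- Size: 88 to 98 per arm (Protocol 5.5 and 10.3).
- Sites: up to 18 (Protocol 5.1.1) or up to 27 (SAP 2).
- R², the share of variance in log normalized TRE explained by covariates: not in the documents, so a range is shown.

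**Power of the non-inferiority test.** SE = SD × √((1 − R²) × 2/n). Power comes from the noncentral t distribution at one-sided 0.025, with one extra degree of freedom spent when R² > 0. For 88 per arm, unadjusted: SE = 0.697 × √(2/88) = 0.105, noncentrality 0.2231/0.105 = 2.12, power 56.1%. Ranges below run from 88 to 98 per arm, SD 0.697, conditional on the primary endpoint being met.

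| True ratio | Unadjusted | R² 0.05 | R² 0.10 |
|---|---|---|---|
| 1.00 | 56-61% | 58-63% | 61-65% |
| 0.95 | 74-78% | 76-80% | 78-82% |
| 0.90 | 88-91% | 89-92% | 91-93% |

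For the reduction hypothesis, a true ratio of 0.80 gives the ratio-1 row again, because ln 0.80 = −0.223. The SD matters more than the adjustment: at ratio 1 and 98 per arm, R² 0 versus 0.10 gives 87.5% versus 90.6% at SD 0.5, and 49.3% versus 53.5% at SD 0.8.

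**How much could stone size explain?** Assume one stone per subject, with diameter 6 + 14 × Beta(1, 4.53) mm. This spans the 6-20 mm eligibility range with mean 8.53 mm, the average of 13 subjects in Protocol 4. The SD of log area is 0.458.
- If energy is proportional to area, dividing by area leaves nothing: R² = 0.
- If energy is proportional to volume (area to the power 1.5), 0.5 × log area remains, with variance 0.25 × 0.458² = 0.0524. In this case 0.697 is the SD after size has been removed, so the area-normalized SD is √(0.697² + 0.0524) = √0.538 ≈ 0.734 and R² = 0.0524/0.538 = 0.097. Power at ratio 1 rises from 51.9% to 56.1% with 88 per arm, and from 56.3% to 60.7% with 98.

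**How much could site explain?** The proposed model was simulated with 12,000 runs per scenario, unequal sites capped at 20%, an assumed block size of 4, total SD 0.697, REML, and N − sites − 2 degrees of freedom. Power at ratio 1, t-test then model:
- Nothing prognostic: 61.5% then 61.6% (196 subjects, 18 sites); 55.9% then 55.8% (176 subjects, 27 sites).
- Site share 10%: 61.2% then 64.3%; 56.5% then 59.5%.

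**Type I error.** If blocking balances the sites and site explains a share s of the variance, the t-test's one-sided error is about 1 − Φ(1.96/√(1 − s)): 0.022 at s = 0.05 and 0.019 at s = 0.10. Simulation at a 10% share gave 0.020-0.023 for the t-test. The adjusted model gave 0.023-0.026 across all scenarios.

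**The case against.** The t-test is a legitimate, simple choice, supported by a Wilcoxon test and a site ANOVA, and nothing about it is invalid. That stands in full. Its error rate is at or slightly below nominal, so a reader who infers an inflated false-positive risk from ignoring the blocking would have the direction wrong.

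Stone size is already in the outcome through the division by area. This also stands: a size covariate helps only if energy is not proportional to area, and the documents do not show that. A reader might carry over the R² of 0.524 quoted in Protocol 10.7 and infer a large gain. That figure is for total energy before normalization and does not transfer.

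Combining a 10% site share with volume scaling gives a simulated rise from 61% to 71% (196 subjects, 18 sites). That figure should not be relied on. It stacks two assumptions, and it holds the total SD at 0.697, which is too low under volume scaling, so its power levels are too high.

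The SAP's statement on covariates might be read as proof that the final TRE analysis is unadjusted. It is not, because that SAP does not cover TRE. The separate plan may already adjust; what stands is the rule written in Protocol 10.5 and 10.7.

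Site terms can also cost precision. With separate fixed site terms that explain nothing, and within-site balance no better than chance, power at 88 per arm could fall from 56.0% to 51.7% (18 sites) or 49.4% (27 sites). This is why the proposal uses a random intercept, which lost essentially nothing in the simulation.

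**Conclusion.** The point holds as a possible precision gain. At a true ratio of 1, covariates that explain 10% of the variance add 4 to 5 points, a 10% site share alone adds about 3, and volume scaling adds about 4 from a lower starting level. At a true ratio of 0.90 the t-test already has 88-91% power and the gain is about 3 points. If neither site nor residual size is prognostic, the gain is zero and the loss negligible.

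All power figures are conditional on the primary endpoint being met. If the endpoints were independent (an assumption), a gain of 4.5 points would become 0.80 × 4.5 = 3.6 points overall.

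The results rest on lognormality, on an SD derived from an approximate quartile ratio, and on an assumed site share and scaling exponent. Study Success does not depend on TRE (Protocol 6.6). This is a recommended improvement, not a required correction.

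**What to change.** Before unblinding, amend Protocol 10.5 and 10.7 and the separate efficacy plan so that both TRE hypotheses are tested from one pre-specified linear model of log normalized TRE in the ITT population:
- Terms: treatment, log total baseline stone area (the same area that normalizes TRE), and a random site intercept fitted by REML.
- State the degrees-of-freedom method, because it sets the bound that is compared with 0.223: for example N − sites − 2, as simulated, or Kenward-Roger.
- State that an estimated site variance of zero reduces the model to ANCOVA without site.
- Compare the upper limit of the two-sided 95% confidence interval for the adjusted difference with 0.223 and then with 0. Report the adjusted geometric mean ratio.
- Keep the planned t-test and Wilcoxon test as sensitivity analyses.

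If the separate plan already specifies an adjusted model, only the Protocol wording needs to be aligned.

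The cost is a few sentences and a few lines of mixed-model code. No new data are needed, and the margin, alpha, testing order and primary analysis do not change. The downside is a slightly less simple model and, if nothing is prognostic, a loss of up to about 1 power point (about 0.1 in the simulation).

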10.8. Additional Observations

Mean total lasering time will be analyzed as a numeric endpoint using the ITT Population. A two- sided t-test with equal variance assumed will be used to evaluate the null hypothesis that mean time is similar in both groups. A 95% two-sided CI for the mean difference will be provided. An ANOVA will be used to evaluate mean total laser time as a function of location, treatment, and location x treatment interaction. Least square means will be provided with ANOVA p-values.

The number and percentage of subjects receiving subsequent additional interventional stone procedures for stone(s) that were treated in the AEROLITH study will be summarized. A Likelihood-Ratio chi-square test will be used to evaluate the null hypothesis that the proportion of subjects with at least one secondary stone treatment is equal in both groups. In addition, the total number of secondary stone treatments will be summarized and a Cochran- Armitage trend test will be used to evaluate the null hypothesis that there is no trend in the number of stones between the groups.

Use and quantity of prescription pain medication for managing stone-associated pain will be characterized by timing and type of medication and will be summarized descriptively for the ITT and PP Population.

Residual stone size will be summarized descriptively as a continuous variable and rate of absence of residual stones as a categorical variable. These will be summarized for the ITT and PP Populations.

11. SAFETY REPORTING

Safety outcomes will be organized into adverse events related to the device, or procedure or unrelated to either, and the severity. All procedure, and post-procedure complications, whether device-related or not will be recorded and all reportable events will be reported. Subject symptoms including pain, neurological, and functional symptoms are expected and are considered adverse events when these symptoms result in an unscheduled visit, new or worsening symptoms, as compared to baseline.

11.1. Adverse Event

An adverse event (AE) is any undesired clinical response or complication experienced by a subject. Monitoring and documenting of adverse events will begin at the start of the index procedure. When an adverse event is recorded as ongoing, an effort will be made to follow-up on the event at subsequent subject visits until the event is resolved or the subject exits the study.

CONFIDENTIAL Page 36 of 53

In this study, adverse events should be reported beginning at the time of administration of general anesthesia for the index procedure. Pre-existing conditions (recorded on the Medical History CRF), which occur during the study at the same severity as in the subject's history, should not be recorded as adverse events. Pre-existing conditions (recorded on the Medical History CRF) that worsen during the study OR a new episode begins must be recorded as AE(s). The onset date should be the start of the current episode or the date of the change in severity, not the onset date recorded on the Medical History CRF.

Upon enrollment, if a new adverse event is reported and subsequently determined to be medical history not previously documented, the information should be added to the medical history CRF. The event should be recorded as an AE only if there was a change in severity.

Intermittent Events

An AE that occurs intermittently at the same severity should be aggregated and recorded as one event unless, in the opinion of the Investigator, the events should be reported as discrete events (medical diagnosis terms).

- The onset date is the start of the first episode during the study.
- The resolution date is the end of the last episode (or may be persistent, if ongoing at the end of the study).
- The site should record "intermittent" in the AE description. If an intermittent event meets the regulatory criteria for seriousness, the associated frequency of the adverse event term (e.g., 4x/week) should be captured in the narrative/comment section of the CRF.
- If the event changes in severity or relationship to study device, it should be recorded as an AE update.

All peri- and post- procedural AEs, whether device- or procedure related or not, will be recorded as an Adverse Event. Data to be collected includes the description of the AE, onset and resolution dates (or whether the AE is ongoing), severity, actions taken, outcome, and determination of the event relationship to the device and/or procedure. In general, AEs should be reported and classified by the Investigator using a diagnosis and not an action taken. The diagnosis should be confirmed through specific signs, symptoms, and (if necessary) laboratory tests.

The Investigator, on the basis of his or her clinical judgment, will determine the relationship of the AE to the device and/or procedure based on the following categories:

- 1. **Unrelated:** The adverse event is determined to be solely caused by the underlying disease, disorder or condition of the subject, or attributable solely to other extraneous causes (unrelated to the device, device malfunction, or the procedure).
- Possibly related: The adverse event has onset within a clinically relevant temporal relationship to exposure to the device or procedure, and is plausibly at least partially caused by or aggravated by the use of the device, device malfunction, or the procedure. It must also meet one of the following criteria: (1) follows a known or easily foreseen pattern of response to device use or procedure and (2) is not fully attributable to the underlying disease, disorder or condition of the subject, or attributable to other extraneous causes.
- 3. **Probably related:** The adverse event has onset within a clinically relevant temporal relationship to exposure to the device or procedure, and is more likely than not to be at least partially caused by or aggravated by the use of the device, device malfunction, or the procedure. It must also meet both of the following criteria: (1) follows a known or easily foreseen pattern of response to device use or procedure; and (2) is not fully attributable to the underlying disease, disorder or condition of the subject, or attributable to other extraneous causes. In addition, if the adverse effect is reversible upon reoperation or device exchange, and such a procedure is done, the effect disappears or lessens in severity within the expected time interval.

CONFIDENTIAL Page 37 of 53

4. Definitely related: The adverse event is clearly caused by the use of the device, device malfunction, or the procedure. It must meet all following criteria: (1) has a clear temporal relationship between device exposure and onset of the event; (2) follows a known pattern of response to device use or procedure; and (3) is not reasonably attributable to the underlying disease, disorder or condition of the subject, or attributable to other extraneous causes.

Severity of an AE will be determined by the Investigator following Common Terminology Criteria for Adverse Events (CTCAE):

Grade 1: Mild; asymptomatic or mild symptoms; clinical or diagnostic observations only; intervention not indicated.

Grade 2: Moderate; minimal, local or noninvasive intervention indicated; limiting age appropriate instrumental Activities of Daily Living (ADL)*.

Grade 3: Severe or medically significant but not immediately life-threatening; hospitalization or prolongation of hospitalization indicated; disabling; limiting self-care ADL**.

Grade 4: Life-threatening consequences; urgent intervention indicated.

Grade 5: Death related to AE.

Note: *Instrumental ADL refer to preparing meals, shopping for groceries or clothes, using the telephone, managing money, etc.

**Self care ADL refer to bathing, dressing and undressing, feeding self, using the toilet, taking medications, and not bedridden.

The term "severe" is used to describe intensity (severity) of a specific event. An event itself, may be of relatively minor medical significance (such as a severe headache). This is not the same as "serious", which is based on subject/event outcomes or action criteria usually associated with events that pose a threat to the subject's life or functioning.

For the purposes of safety reporting in this study, the following definitions will be applied:

- An **Adverse Event** (AE) is any untoward medical occurrence in a subject whether it is considered device related or not. Diseases, signs, symptoms, or laboratory abnormalities already existing at enrollment are not considered AE's unless they worsen (i.e., increase in intensity or frequency). Surgical procedures themselves are not adverse events; they are therapeutic measures for conditions that require surgery. The condition for which the surgery is required may be an adverse event. Surgical procedures planned prior to enrollment and the conditions leading to these measures are not adverse events.
- An Adverse Device Effect (ADE) is any untoward and unintended response to a medical device, including events arising from insufficient or inadequate instructions for the employment of the device or its use.
- A Serious Adverse Event (SAE) is any AE that:
 - results in death;
 - is life threatening;
 - results in or prolongs hospitalization;
 - results in permanent impairment of a body function or permanent damage to a body structure;
 - necessitates medical or surgical intervention to preclude permanent impairment of a body function or permanent damage to a body structure;

Note: For the purposes of this protocol, for a subject who has been treated with standard URS-LL or with Acoustic Enhancer with URS-LL and requires an additional treatment to further fragment or eliminate the stone, this additional procedure will not be considered an adverse event.

- Led to fetal distress, fetal death, or a congenital abnormality or birth defect;
- Other serious medically important event.

Note: Planned hospitalization for a pre-existing condition, or a procedure required by the CIP, without serious deterioration in health, is not considered a serious adverse event

• An Unanticipated Adverse Device Effects (UADE):

The investigational device exemption (IDE) regulations and ISO 14155:2020 (Clinical Investigation of medical devices for human subjects – Good clinical practice) defines an unanticipated adverse device effect (UADE) as any *serious* adverse effect on health or safety, any life-threatening problem or death caused by, or associated with a device, if that effect, problem, or death was not previously identified in nature, severity, or degree of incidence in the clinical investigational plan or risk analysis; or any other unanticipated serious problem associated with a device that relates to the rights, safety, or welfare of subjects" (21 CFR Part 812.3(s)). UADEs must be reported by the clinical investigator to the sponsor and the reviewing IRB, as described below:

- Investigators are required to submit a report of a UADE to the sponsor and the reviewing IRB as soon as possible, but in no event later than 10 working days after the investigator first learns of the event (21 CFR Part 812.150(a)(1)).
- The Sponsor will immediately conduct an evaluation of a UADE and report the results of the evaluation to the appropriate regulatory agency, all reviewing IRBs and participating investigators within 10 working days after first notice of the effect (21 CFR part 812.46(b), 812.150(b)(1)).

ALL SERIOUS ADVERSE EVENTS AND UNANTICIPATED ADVERSE DEVICE EFFECTS OCCURRING THROUGHOUT THE STUDY MUST BE REPORTED TO THE SPONSOR OR ITS DESIGNEE AND MUST BE RECORDED IN THE EDC SYSTEM WITHIN 24 HOURS OF FIRST LEARNING ABOUT THE EVENT.

The investigator is required to notify the IRB of SAEs in accordance with IRB reporting requirements.

All subjects will be followed at 14 and 30 days post procedure.

Note 1: Subjects with new and on-going device and/or procedure-related serious adverse events at 30 days post procedure will be followed until the event has resolved or deemed stable by the investigator.

Note 2: Subjects with new and on-going hydronephrosis and subjects with pre-existing (prior to treatment) hydronephrosis that has worsened or recurred since baseline at 30-days post procedure will continue to be followed through 90 days.

Note 3: At 90-days post procedure, subjects who have on-going device and/or procedure-related serious adverse events (including device and/or procedure related hydronephrosis) and subjects with pre-existing (prior to treatment) hydronephrosis that have worsened or recurred since baseline, will continue to be followed until the event has resolved or until the investigator deems the event is stable prior to study exit. If the events are deemed stable by the investigator, the investigator should refer the subject for further care to the subject's primary provider or urological specialist upon exiting the study.

CONFIDENTIAL Page 39 of 53

